
Target population: Restricted to the primary school pupils
	
By the start of the school year 2021-2022, vaccination age might have been changed for 12 year olds and older. Therefore we limit the study extension to primary school pupils.
 
We do not foresee to include new schools to the study. In case of decreased participation in the school, we will recruit additional pupils up to a maximum of 25 pupils per school to secure a sufficient sample size for the point seroprevalence estimates.
	
2. Objectives 3. Methods 3.2. Study design 3.6. Data collection 3.6.1. Data collection procedure 3.6.3. Laboratory specimen collection, transport and analysis – serological test 3.6.5. Special considerations and circumstances 7. Protection of human subjects and Ethical considerations 7.1. Informed consent 7.6. Study insurance

Additional questions:
	
In the questionnaire that is part of the study and has to be completed by the parents questions on relatives' and (if relevant) child vaccination status will be added.
	
Appendix b: Additional questions to be added at questionnaire for parents

Additional document: New informed consent parents
		
Appendix d: Informatie- en toestemmingsformulier (NL+FR) – separately attached

Changes November 2020:

Change / addition	Rational	Affected protocol section

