This study will make it possible to better describe the prevalence of circulating antibodies in children and school staff in Belgian primary and secondary schools as well as the incidence of new infections in this subpopulation since they will be followed for 7 months. Additionally, by also questioning household members in the case of the children and by questioning the school staff, we will gain a more in-depth insight in symptomatic COVID-19 disease within households in Belgium, by linking the results of the salivary antibody tests in symptomatic and asymptomatic children with disease information of household members. The study also aims to generate insights in the clinical presentation of the disease among school-aged children and school staff and to evaluate the effect of child behaviour (e.g. participation in outside school activities) on the infection rate among children.

The study will cover all regions¹ in Belgium (Brussels-Capital, Flemish and Walloon Region) and interim data from each wave can guide the Belgian policy makers and CELEVAL (Group of Belgian Experts in charge of COVID-19 related public measures) in their advice on specific COVID-19 related measures for school-age children in order to limit circulation of SARS-CoV-2 in Belgium and to prevent an overload of our healthcare system with a limited societal impact (e.g. school closures). This data might also guide the expert group who will give advice regarding vaccination strategies whether children should be included for vaccination to create herd immunity or not.

¹ A stratified selection of all of all municipalities.

2. Objectives

Main objective

To determine the prevalence and incidence of antibodies against SARS-CoV-2 in a sample of school-aged children and school staff (primary and secondary school) and primary school children only in Belgium at different time points.

Secondary objective

- Determine the cumulative incidence of SARS-CoV-2 from baseline to 7 months in the complete sample and 1 year among primary school children
- Determine the proportion of asymptomatic infections with SARS-CoV-2 in this sample
- Gain insight in the role of COVID-19 infection in household members of children and school staff in this sample
- Describe child characteristics and investigate potential risk factors for infection among school-age children
- Describe characteristics of school staff and investigate potential risk factors for infection among school staff

Exploratory objective

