3.2. STUDY DESIGN

This study will be set up as a prospective cohort study.

Children and school staff will be recruited at the 1st testing period in the participating school. Samples will be taken within a timeframe of maximum 4 weeks for all the participants.

Parents/legal child caregiver and staff will need to complete a questionnaire at each of the testing moments providing basic socio-demographic characteristics (at baseline only) and risk-behaviour and health characteristics including presence of symptoms during the time since the previous testing period (at each of the testing periods). The questionnaire will be completed ~~by a parent of caregiver~~ through a secured online application during the same week as the collection of a saliva sample. ~~from the child.~~

The study will last 12 months. There will be in total 3 testing periods when data and sample collection will be performed for the total study population; in ~~October~~ December 2020 (Baseline), ~~January~~ February 2021 (M3) and April/May 2021 (M6). There will be a 4th and 5th testing period for primary school pupils only: in September 2021 (M9) and December 2021 (M12).

Saliva samples will be sent to the Sciensano laboratory for analysis. Serological test results will be communicated to the child's parent/legal caregiver by a closed letter through the participating school.

Epidemiological data analysis will be performed and reported after each testing period and at the end of the study.

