3.7. DATA ANALYSIS

The analysis will be descriptive for the primary objective. Variables will be described as proportions with a 95% Confidence Interval (95%CI). Several epidemiological parameters/effect measures will be calculated with a 95%CI.

Among others:

- Seroprevalence of SARS-CoV-2: number of children/ number of school staff in whom specific SARS-CoV-2 antibodies was detected by ELISA / total number of children/staff tested.
- SARS-CoV-2 seroconversion rate: Number of children/ number of school staff in whom presence of specific antibodies was detected by ELISA during any of the follow-up tests with a previous sample showing no specific antibody / total number of children/staff followed-up with a baseline negative serum sample, during the study period of 7 months.
- Cumulative incidence
- Incidence rates (using both the total population and the population excluding the non-susceptible from the prior sero-survey testing period)
- Proportion of asymptomatic cases
- Proportion of symptomatic episodes amongst positives versus negatives

A flow diagram of the participants will be created reflecting number of participants approached, eligible and included. The statistical analysis will account for the small differences in sampling probability due to the study design by using specialized procedures for complex (survey) sampling..

For the secondary objectives, uni- and multivariate analysis will be performed assessing risk, protective and predictive factors associated with sero-positivity among children and among staff. Relative risk of sero-positivity in function of specific risk factors (prior to analysis a directed acyclic graphs (DAG) will be constructed and risk factors will be analysed using Poisson regression and effect

measures will be re-calculated and presented as absolute risks and risk differences with their CI). Models will be assessed for presence of confounders and interaction.

When tables will be presented e.g. test positives versus test negatives at the end of the study, no p-values will be presented comparing differences in basic characteristics to avoid chance-findings.

A sensitivity analysis will be performed to estimate bias resulting from the imperfect accuracy of serology testing. If needed other sensitivity analysis will be performed and selection bias will be assessed. Depending on the amount of missing data imputation will be used.

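### The seroconversion rate is not a valid risk as written: its numerator and denominator have different entry conditions, and cumulative incidence has no formula

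*Combined protocol and SAP*

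**What the plan says.** Section 3.7 gives only one incidence measure both a numerator and a denominator, the seroconversion rate. Its numerator is the children or staff "in whom presence of specific antibodies was detected by ELISA during any of the follow-up tests with a previous sample showing no specific antibody". Its denominator is the "total number of children/staff followed-up with a baseline negative serum sample, during the study period of 7 months".

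Cumulative incidence is a separate bullet in the same list, without a formula, although section 2 sets the objective "Determine the cumulative incidence of SARS-CoV-2 from baseline to 7 months in the complete sample and 1 year among primary school children". Incidence rates are a third bullet, to be computed "using both the total population and the population excluding the non-susceptible from the prior sero-survey testing period".

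Four other provisions bear on the point:
- The inclusion criteria in section 3.1 require presence at the first testing period.
- The July 2021 table of changes says that if participation falls, "we will recruit additional pupils up to a maximum of 25 pupils per school"; the purpose given is the point seroprevalence estimates.
- Section 3.7 foresees imputation, depending on how much is missing, with no method or target variable.
- Section 5 promises a data analysis plan.

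**The concern.** A risk is a proportion: everyone counted on top must also be counted below, and everyone below must have been observed long enough to become a case. The stated ratio breaks the first rule and, on its literal reading, the second.

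- **Numerator wider than denominator.** Someone positive at baseline, negative at M3 and positive at M6 has an earlier negative sample and so is a seroconverter, but has no negative baseline and so is not in the denominator. This pushes the ratio up.
- **Early leavers.** Someone negative at baseline and at M3 who misses M6 has been followed up, in the ordinary sense of the word. That person stays in the denominator as a non-converter for the whole period. This pushes the ratio down.

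Seroconversion is part of the main objective in the synopsis, and sero-incidence and cumulative incidence are secondary outcomes. Because the errors oppose each other and depend on attrition and seroreversion, a reader could not recover the size or the sign of the net error from the published ratio.

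**Working it through.** The documents give no expected seroconversion figure to reproduce. The sample size used below does reproduce: 400 × 2 / 41 = 19.51, rounded to 20, and 20 × 41 = 820 children per age group (section 3.3).

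**1. Positive-negative-positive from test error alone**

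Inputs: n = 820 and prevalence p = 6.0% (section 3.3); sensitivity Se = 95.9% and specificity Sp = 98.6% (section 3.6.3). Assumptions: errors independent between tests, no true change in serostatus, everyone tested three times. The documents report no accuracy for saliva, so these values stand in for it.

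- P(+,−,+) = p·Se·(1−Se)·Se + (1−p)·(1−Sp)·Sp·(1−Sp) = 0.06 × 0.959 × 0.041 × 0.959 + 0.94 × 0.014 × 0.986 × 0.014 = 0.00226 + 0.00018 = 0.00244, which is 2.0 people in 820.
- P(baseline negative) = 0.06 × 0.041 + 0.94 × 0.986 = 0.9293, which is 762 people.
- Addition to the ratio: 0.00244 / 0.9293 = **0.26 points**.

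With the 88% sensitivity that section 3.6.3 also reports (more than 21 days after PCR confirmation), it is 4.7 people and 0.62 points. For 820 staff at the 10% prevalence of section 3.4, with 95.9% and 98.6%, it is 3.2 people and 0.44 points.

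**2. The same sequence from true seroreversion**

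The documents give no rate. Let a share s of the 820 × 0.06 = 49.2 baseline positives turn negative and a share r of those turn positive again; the baseline negatives number 770.8. The addition is 49.2·s·r / 770.8:

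| s | r | addition (points) |
|---|---|---|
| 10% | 10% | 0.06 |
| 20% | 50% | 0.64 |
| 30% | 96% | 1.84 |

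**3. Early leavers over the stated 7 months**

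Three tests make two intervals. Assume equal risk h per interval and loss d per interval, unrelated to infection. Those lost before M3 have no follow-up sample and leave both counts. The literal ratio is h + (1−h)(1−d)h, and the true risk is 1 − (1−h)².

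For a true risk of 10%, h = 1 − √0.90 = 0.0513:

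| d | literal ratio |
|---|---|
| 5% | 0.0513 + 0.95 × 0.0487 = 9.8% |
| 10% | 0.0513 + 0.90 × 0.0487 = **9.5%** |
| 15% | 0.0513 + 0.85 × 0.0487 = 9.3% |

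At h = 6% the true risk is 11.64%; losses of 10%, 20% and 30% give 11.08%, 10.51% and 9.95%. The interval-by-interval product, 1 − 0.94 × 0.94 = 11.64%, is unaffected by loss of this kind.

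**4. Both together (h = 6%)**

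- d = 10%, s = 20%, r = 50%: 11.08 + 0.64, about 11.7% (11.71% unrounded), against a true 11.64%.
- d = 20%, s = r = 10%: 10.51 + 0.06, about 10.6%.
- d = 20%, s = 30%, r = 96%: 10.51 + 1.84 = 12.35%.

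The sign is not fixed, and near-cancellation in the first case is an accident of the inputs.

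**5. Only if the ratio were carried to 12 months**

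With four intervals and a true 10% risk, h = 1 − 0.90^(1/4) = 2.6%. Loss of 5%, 10% or 15% per interval gives 9.3%, 8.6% or 8.0%. For top-ups, the documents give a ceiling per school but no expected number. Per 100 top-ups, assuming 85% negative in September and the same 2.6% converting by December, 100 × 0.85 × 0.026 = 2.2 people enter the numerator alone, against 762 × 0.10 = 76 events, about +3%.

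**The case against.** The best defence is that this is loose wording that a competent analyst would read correctly, with a data analysis plan still to come. The primary outcome, seroprevalence at each time point, is untouched. The 7-month effects are small beside sampling error: at 10% risk with 762 baseline negatives and the planned design effect of 2, the 95% half-width is 1.96 × √(2 × 0.10 × 0.90 / 762) = 3.0 points, against 0.26 and 0.5 points here. If *followed-up* means tested at every period, early leavers drop out altogether.

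Most of this stands as a limit on size. It does not remove the defect. The mismatch is in the text and needs no assumption. The complete-follow-up reading exchanges one problem for complete-case selection, and the plan does not say which is meant. Conditional imputation without a method does not define a risk set, and the planned sensitivity analysis for test accuracy does not redefine one.

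A reader might infer more than the documents support:
- **That reported cumulative incidence is biased.** Section 3.7 lists it apart from the seroconversion rate and gives it no formula. It is undefined, and would be biased only if this ratio were used for it.
- **That top-up pupils distort the stated ratio.** The formula is limited to 7 months, and entry in that period requires presence at the first test. Top-ups matter only for a 12-month version.
- **That the incidence rates return seroreverted children to the risk set.** The second version uses "the population excluding the non-susceptible from the prior sero-survey testing period", but *non-susceptible* is not defined as currently seropositive, so the text does not force this.
- **That carried-over positives will be called asymptomatic.** Follow-up questionnaires cover health "including presence of symptoms during the time since the previous testing period", but they are completed at every period and linked by identifier, so earlier symptoms are on file. Nothing says that only the latest questionnaire decides.

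**Conclusion.** The point holds in a limited form. As written, the seroconversion rate is not a proper risk. That rests on the wording alone for the numerator, and on the literal sense of *followed-up* for early leavers.

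Within the stated 7 months the size is modest. It is about +0.26 points from test error at the protocol's accuracy and 6% prevalence, more if antibodies wane and return, and about −0.5 points at a true 10% risk with 10% loss per interval. Loss, seroreversion and re-positivity rates are assumptions, and loss is taken as unrelated to infection. The net direction cannot be stated in advance.

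The larger gap is that 7-month and 1-year cumulative incidence are objectives with no estimator, while the only explicit ratio nearby is the defective one. This should be settled before the incidence analyses are run. It does not threaten the primary outcome.

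**What to change.** In section 3.7 or the data analysis plan:

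1. Restrict numerator and denominator to the same baseline-negative participants, and count the first positive after all-negative samples.
2. Define *followed-up*, and state how positive-negative-positive sequences and missed tests are handled.
3. Give cumulative incidence a formula at 7 months and, for primary pupils, at 1 year. Take as the risk set for each interval those negative on every earlier sample and tested at its end, and report one minus the product of the interval-specific non-conversion proportions. An interval-censored estimator is an alternative. Use the survey weights and allow for clustering by school.
4. Leave September 2021 top-ups out of baseline-to-12-month counts, or let them enter at their own first negative sample.
5. While the text is open, define *non-susceptible* for the incidence rates and say which questionnaires determine asymptomatic status.

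The cost is wording and a few lines of code. Serial results are already held for each participant, so no new data are needed.

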- Children primary schools: any pupil from the 3rd grade (or from the 2nd grade if not enough participants from 3rd grade are available in the selected school) who regularly attend school and is present at school at the first testing period
- Children secondary schools: any pupil from 2nd grade who regularly attend school and is present at school at the first testing period
- Staff primary schools: any teaching or supporting/none-teaching staff (e.g. administrative staff) having contact with pupils and is present at school at the first testing period
- Staff secondary schools: any teaching staff teaching at least also in the 1st or 2nd grade of the secondary school and is present at school at the first testing period
- Prior known SARS-CoV-2 infection does not exclude participation

Exclusion criteria:

- Pupils or staff who refuse to have the saliva sample taken
- For children: being a sibling of a study participant

- A close family member included in the study: only one member per nuclear family will be included in the study
- No informed consent form signed (by parent of legal caregiver) available at the recruitment

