Data analysis will be done by KUL (statistician) and Sciensano using statistical software already available to the analysis team (including STATA 14/ SAS/ R), while having the necessary licenses.

4. Expected outcome

Primary outcome: SARS-CoV-2 seroprevalence at each time point

Secondary outcomes:

- SARS-CoV-2 sero-incidence and seroprevalence over time
- Cumulative incidence
- Proportion of symptomatic sero-positive cases
- Participants characteristics associated with test-positivity

Findings will help to understand the dynamics of COVID-19 among children and support the implementation of preventive and other measures for this population group.

5. Quality assurance

The protocol will be reviewed by the different partners and published on Clinicaltrials.gov.

Questionnaire contents and tool will be piloted for understandability and to check if the tool functions well. Study nurses responsible for sample collection will be trained. Laboratory analysis will be performed at the Sciensano laboratories. A validation study of the oral swabs will be performed prior to the start of the study to assure the validity of the specimen sample among children. A data analysis plan will be available.

6. Potential Biases and limitations

Selection bias

- Due to feasibility choices. For example, participants ~~children~~ chosen will not be completely representative of the school-age children and school staff population of Belgium. This will be documented by comparing characteristics of the participants with census data and other data sources.
- Exclusion bias: Due to non-consent to the study. The non-consent rate will be calculated to estimate the importance of this bias.

Cluster bias (non-independence of events)

If the selected participants belong to the same group (same class, same school, same family, etc.), this can affect the risk of seroconversion. This effect will be minimized by the multiplicity of contact points investigated, correction of the sample size for the number of clusters and the exclusion of multiple children from the same household.

Information bias

- Misclassification
- Imperfect accuracy (and imperfect reference standard for corrections): sensitivity analysis can be performed correcting for imperfect accuracy of serological testing
- Precision - depending on prevalence

Confounding

- Unmeasured confounders.
- Confounders will be investigated using DAG's and adjusted for where justified.

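### The risk-factor models use sero-positivity as outcome at follow-up rounds without excluding earlier positives, although the question is risk of infection and the cohort observes seroconversion

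*Combined protocol and SAP*

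**What the plan says.** The objective in section 2 is "Describe child characteristics and investigate potential risk factors for infection among school-age children", with a parallel objective for staff. For these secondary objectives, section 3.7 specifies univariate and multivariate models "assessing risk, protective and predictive factors associated with sero-positivity among children and among staff". The effect measure is "Relative risk of sero-positivity in function of specific risk factors", estimated by Poisson regression and re-expressed as absolute risks and risk differences. Section 4 lists the matching outcome as "Participants characteristics associated with test-positivity". None of these statements restricts the models to participants who were negative before.

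Three other provisions bear on this:

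- **Entry (section 3.1).** "Prior known SARS-CoV-2 infection does not exclude participation".
- **Exposure data (section 3.2).** The questionnaire at each round collects "risk-behaviour and health characteristics including presence of symptoms during the time since the previous testing period". Demographic and socio-economic data are collected at baseline only.
- **Conversion (section 3.7).** A seroconversion rate is defined with denominator "total number of children/staff followed-up with a baseline negative serum sample, during the study period of 7 months". Incidence rates are to be computed both in everyone and in those still susceptible after the previous round. Both appear in the list of descriptive parameters, and neither is named as the outcome of the risk-factor models.

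**The concern.** A risk factor for infection has to act before the infection. A positive antibody result at a follow-up round mixes infections acquired since the last test with infections already detected earlier. For the second kind, behaviour, contacts or household illness reported for the recent period come after the event they are meant to explain.

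Two effects can follow. If recent exposure is unrelated to the old infection, the old cases dilute the contrast and pull the relative risk toward 1. If it is related because of the infection, the bias can go either way. That route is plausible here: known past infection is allowed at entry, and section 3.6.3 returns individual results after each round, so a family may know the child is positive before answering the next questionnaire.

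The findings are meant to support preventive measures (section 4). Real behavioural, household or school-related risks could look weaker than they are, or be misdirected.

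**Working it through.** **The plan's own figures.** No figure is given for the risk-factor models. The sample-size figures for children (section 3.3) reproduce: 1.96 × √(0.06 × 0.94 / 400) = 2.33% against the stated 2.3%; 400 × 2 / 41 = 19.51, rounded to 20; 41 × 20 = 820 per age group. No stated number is in error.

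**Inputs from the plan.** 820 children per age group, design effect 2, and the planning seroprevalence of 6.0%, used here as baseline prevalence p0 (an assumption).

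**Assumed, not in the documents.** Conversion risk I over follow-up of 3% to 14%; half the children exposed; true relative risk of conversion 2.0; later exposure independent of pre-baseline infection; antibodies persist; perfect test.

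**Formulas.**

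- Baseline positives: 0.06 × 820 = 49. At risk: 771.
- Share of ever-positives that predate baseline: p0 / [p0 + (1 − p0) × I].
- Conversion risk in the unexposed: I0 = I / 1.5. In the exposed: I1 = 2 × I0.
- Relative risk seen with sero-positivity as outcome: [p0 + (1 − p0) × I1] / [p0 + (1 − p0) × I0].
- Power: two-proportion normal approximation, two-sided 5%. The effective number per exposure group is 820 / 2 / 2 = 205 for sero-positivity and 205 × 0.94 = 192.7 for conversion.

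Example at I = 6%: share = 0.06 / (0.06 + 0.0564) = 0.515. With I0 = 0.04 and I1 = 0.08, the relative risk seen is 0.1352 / 0.0976 = 1.39.

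| Assumed I | Converters among 771 | Share predating baseline | RR seen (true 2.0) | Power, sero-positivity | Power, conversion |
|---|---|---|---|---|---|
| 3% | 23 | 68% | 1.24 | 10% | 21% |
| 6% | 46 | 51% | 1.39 | 22% | 38% |
| 10% | 77 | 39% | 1.51 | 42% | 59% |
| 14% | 108 | 31% | 1.59 | 62% | 75% |

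At p0 = 10%, the planning value for staff in section 3.4, the share runs from 79% down to 44% and the relative risk seen from 1.15 to 1.46.

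**Test error in the alternative outcome.** Section 3.6.3 gives specificity 98.6% and sensitivity 95.9% for the assay. Assume these hold for saliva and that those negative at the previous test are truly negative.

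- At 3% conversion in an interval, false conversions are 0.014 × 0.97 = 0.0136 and true ones 0.959 × 0.03 = 0.0288, so 32% are false. A true relative risk of 2.0 becomes (0.959 × 0.04 + 0.014 × 0.96) / (0.959 × 0.02 + 0.014 × 0.98) = 0.0518 / 0.0329 = 1.57.
- At 5%, 22% are false and the relative risk seen is 1.69.

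The sero-positivity model at the same conversion risks gives 1.24 and 0.1227 / 0.0913 = 1.34 even with a perfect test.

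**The case against.** **Rounds and pairing are not stated.** Section 3.7 does not name the rounds modelled, say whether they are pooled, or say which questionnaire goes with which result. Results and questionnaires are linked per person, so pairing a result with an earlier questionnaire is compatible with the text. A reader might infer that the plan commits to counting a December 2020 positive again in February and in April/May 2021 against later behaviour. The documents do not say that. They set the outcome and leave the rest open.

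**The recall window is ambiguous.** In section 3.2 the phrase about the time since the previous round may govern symptoms only. Section 3.6.2 gives no window for behaviour or contacts, and the main questionnaires are not in the text available.

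**Not every factor is affected.** A reader might conclude that exposure and outcome are in the wrong order for every earlier positive, or that all the relative risks are biased. Fixed baseline characteristics mostly precede infection, and at baseline only prevalent positivity can be analysed.

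**The attenuation may be smaller.** Habitual activities and household structure persist, so later exposure is partly a proxy for earlier exposure. Waning, which the July 2021 table of changes anticipates, would remove some old positives. Reversal of an association is possible, but no figure supports it.

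**Other provisions exist.** A directed acyclic graph is required before analysis, further sensitivity analyses are allowed, and section 5 promises a data analysis plan.

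The first four points limit the claim and are accepted. The last does not remove it. Confounder adjustment and the accuracy analysis leave the outcome unchanged, and the documents at hand state that outcome as sero-positivity in two places.

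**Conclusion.** The concern holds for time-varying exposures analysed at follow-up rounds. The stated outcome does not match the objective there, and a better-matched outcome is already defined among the descriptive parameters.

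The size depends on conversion risk, which the documents do not give. The range in the table is an illustration under the listed assumptions, not an estimate of bias in this study, and independence of later exposure from earlier infection is the most influential of them. Conversion is not an error-free outcome either, but it remains less attenuated than sero-positivity after allowing for the quoted specificity. In these scenarios it also has more power despite the smaller sample. The matter is worth settling before the models are fitted, because the child and staff risk-factor objectives rest on them.

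**What to change.** In section 3.7, for follow-up rounds:

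1. Define the risk-factor outcome as seroconversion between consecutive tests among participants negative at the previous test.
2. Regress it on the exposures reported for that same interval, and state the recall window and the questionnaire used. Use Poisson regression with intervals pooled, a period term and school-clustered variance.
3. Keep the sero-positivity model for baseline, labelled as association with past infection, and show it alongside for fixed factors.
4. Apply the planned test-accuracy sensitivity analysis to the conversion model too.

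The cost is wording and one further model on data already collected. The plan should state the downsides. Baseline positives (about 49 per age group of children at 6%) do not contribute, nor do participants without a previous result for an interval, such as those who missed a round or replacement pupils entering in the extension. When conversion is rare, a noticeable share of apparent conversions is false, about 22% to 32% in the calculation above.
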